### 3.3 Estimated Study Duration

The Screening period is 30 days, treatment and observation period is from Day 1 to Day 29, and the follow-up period is through Day 180 (6 months from study vaccination). The maximum possible study duration for an individual is 210 days.

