### **5.19 Early Discontinuation**

An individual subject is considered to undergo Early Discontinuation if the subject stops study participation before the Day 180 visit.

An enrolled subject may voluntarily withdraw consent for further participation at any time before the Day 180 visit. The Investigator will request (but cannot require) such subjects to provide the reason(s) for withdrawal of consent and to undergo an Early Discontinuation visit.

In addition, the Investigator, at his or her discretion, may withdraw a subject from further participation in the study. Criteria for withdrawal by the Investigator include:

- Noncompliance with the protocol
- Pregnancy
- Immediate hypersensitivity reaction associated with a study injection
- Loss to follow-up – requires documentation of at least 3 unsuccessful attempts to contact the subject. Lost to follow-up will be determined after the date of the subject's projected last visit.
- Other reason(s) which, in the opinion of the Investigator, indicates that continued participation in the study is not in the best interest of the subject.

The Investigator or designee must report any early discontinuation for safety reasons to the Medical Monitor or designee within 24 hours of discontinuation. Additional information regarding ongoing AEs may be provided as a follow-up report.

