#### **6.1.6 Months 3, 4, 5, 6 (90 to 180 days after Day 1 ( $\pm$ 5 days))**

These visits are follow-up phone calls for safety evaluation. The following procedures will take place at each visit:

- SAE, NOCI, and MAAE evaluation
- Concomitant medications or vaccines potentially related to SAE, NOCI, MAAE, or prohibited medications

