##### **7.5.1 Reporting Periods**

The four reporting periods for solicited AEs begin immediately after study vaccine administration and continue for 7 days after the injection. The reporting period for unsolicited AEs is immediately after study vaccine administration on Day 1, continuing through Day 29. AEs that correspond to solicited AE terms but occur outside of (or continue past) the solicited AE collection periods are also collected through the unsolicited AE reporting periods. The reporting period for SAEs begins at the time of informed consent and continues for the duration of study participation.

A summary of the reporting periods is presented in [Figure 3](#).

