6.2.6. Missing, Unused, and Spurious Data

Binary endpoints / Continuous data:

Missing data are assumed to be missing at random and ignorable. Missing data will not be estimated or imputed. Denominators for percentages will be based only on the number of subjects with non-missing values. The only exception is:

- Systemic Solicited AEs with missing “Relationship to study vaccine” will be analyzed as “Possibly related”.

Dates:

For partial or missing AE start dates the following imputation rules will be applied:

1. If year is not missing and is after the year of first dose:
 - a. If month is missing, then month will be imputed as January.
 - b. If day is missing, then day will be imputed as the first of the month.

2. If year is not missing and is the same as the year of the first dose:
 - a. If month is missing, then impute the month as the month of the first dose date.
 - b. If day is missing, and the month is the same as the month of the first dose date, then impute day as the day of the first dose date.
 - c. If day is missing but month is after the month of first dose date, then impute day as the first day of the month.
3. If year is missing, then impute the year as the year of the first dose date:
 - a. If month is missing, then impute the month as the month of the first dose date.
 - b. If day is missing, then impute the day as the day of the first dose date.
4. If the start date is completely missing, but the AE is either ongoing (i.e. AE stop date is missing) or the stop date is after the first dose date then impute the start date as the first dose date.
5. For any cases involving the rules above, if the AE end date is before the AE start date, then do not impute the AE start date and assume that the AE is treatment emergent/concomitant for the purpose of the analysis. Further, if the AE stop date occurs prior to the first dose date, do not impute the AE start date, and assume that the AE is not treatment emergent.

No imputations will be applied to AE stop dates or other dates. As indicated above, AEs with missing stop date are considered ongoing.

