6.5.1. Adverse Events

6.5.1.1. Solicited Adverse Events

Solicited AEs are protocol-specified local and systemic symptoms/events that are proactively collected from the subject and evaluated by the Investigator or designee. Solicited AEs are collected for 7 days after each injection, starting on Day 1, within an electronic diary. All solicited AEs will be considered “Probably related” to study vaccine.

Solicited AEs for this study are:

- Local events: Pain, Erythema (redness) at the injection site, Edema (swelling) at the injection site
- Systemic events: Fever (oral temperature $\geq 100.4^{\circ}\text{F}$), Fatigue, Headache, Muscle pain, Joint pain

The Subject and the Investigator will grade all AEs for severity from “mild” (grade 1) to “potentially life-threatening” (grade 4), except for severity of redness and swelling recorded as diameters (cm) and graded accordingly (see Guidance for Industry Toxicity Grading Scale for Healthy Adult and Adolescent Volunteers Enrolled in Preventive Vaccine Clinical Trials, September 2007 for details on grading scale).

Only Solicited AEs collected in the eDiary CRF, within 7 days after vaccine administration (i.e. from Day 1 to Day 7) will be analyzed in this Section. Occurrence of a solicited AE on a specific Day will be identified by a Grade ≥ 1 for that AE on that day.

Solicited AEs continuing beyond 7 days after injection will be combined with unsolicited AEs and described separately as specified in Section 6.5.1.3.

The following characteristics will be calculated:

- Maximum severity (Investigator):

For each solicited AE collected for a subject, the maximum severity will be the highest grade recorded, as per Investigator, for all occurrences of this AE within 7 days of vaccine administration (i.e., from Day 1 post-administration to Day 7) for the overall summary, or within a single day for the summary by day. There will be no replacement in case of missing Grade.

- Maximum relationship (Investigator):

For each unsolicited AE collected for a subject, the maximum relationship will be the strongest relationship, as per Investigator, for all occurrences of this AE. There will be no replacement in case of missing relationship.

- Time of first onset of first event (days):

Day of onset of the first solicited AE, as per the nominal visit where the first solicited AE was first reported. This will range from 1 (Day 1 = Day of study vaccine administration) to 7 (Day 7).

- Duration of solicited AEs (days):

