Number of days between the onset of the solicited AE (i.e. nominal visit of first occurrence of Grade \geq 1) and the end of the solicited AE (i.e. nominal visit when Grade is back to 0).

If there are different occurrences of a same solicited AE within 7 days, the durations will be added up.

For solicited AEs continuing beyond 7 days, the end day of the continuing event will be used as end day for the calculation.

Example: If a subject has a Fatigue starting on Day 2 and finishing on Day 3. And a new Fatigue starting on Day 7 and ending on Day 9. The Duration will be 1+2=3.

If the solicited AE is ongoing (i.e. stop date is missing), then duration will be the Number of days between the onset of the solicited AE and the study discontinuation date.

Frequencies and percentages of subjects experiencing each solicited AE will be presented overall and by maximum severity. Summary tables showing the occurrence of any local or systemic solicited AE overall and at each time point will also be presented. For each of the time points or time intervals presented in the summaries, only subjects with at least one observation (ie, any non-missing values but excluding “Not done/unknown”) for the solicited AEs will be summarized.

The following summaries of subjects will be performed:

- [P] Solicited AEs within 7 days post-injection, for each event and for any event, overall and by maximum severity. Details by category (local, systemic) will also be presented. (Severity as per Investigator)
- Solicited AEs by day post-injection, for each event and for any event, overall and by maximum severity on that day. (Severity as per Investigator)
- Solicited AEs by day post-injection, for each event and for any event, overall and by maximum severity on that day. (Severity as per Subject)

- Time of first onset of solicited AEs within 7 days post-injection for each event and any event. Duration of solicited AEs, after injection, for each event. Maximum duration of any event. (Severity as per Investigator)

Listings of all solicited AEs will be provided by subject.

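### The duration of a solicited AE with no stop date runs to an undefined study discontinuation date, so the same event can count as a few days or about six months

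*SAP*

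**What the plan says.** SAP 6.5.1.1 counts the duration of a solicited AE from the diary day on which it first reaches Grade 1 to the day on which the grade returns to 0. Separate occurrences are added together. For an event that outlasts the 7-day diary, its later end day is used. If the stop date is missing, the event counts as ongoing and "then duration will be the Number of days between the onset of the solicited AE and the study discontinuation date". There is no cap, no censoring flag and no separate display. The planned output gives the duration of each event and the maximum duration of any event.

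SAP 6.2.6 repeats that "AEs with missing stop date are considered ongoing", in the same paragraph that rules out imputing AE stop dates.

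Neither document defines the study discontinuation date. The nearest texts are these:

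- Protocol 5.19 counts a subject as an Early Discontinuation "if the subject stops study participation before the Day 180 visit".
- Protocol 5.19 also says: "Lost to follow-up will be determined after the date of the subject's projected last visit".
- Protocol 3.3 runs follow-up through Day 180.
- SAP 5.2 defines an End of Study Visit by the last recorded visit, but SAP 6.5.1.1 does not use that term.

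On how long symptoms are observed, Protocol 7.5.1 states: "The reporting period for unsolicited AEs is immediately after study vaccine administration on Day 1, continuing through Day 29". The Month 3 to 6 calls in Protocol 6.1.6 cover SAEs, NOCIs and MAAEs. Protocol 7.4 separately requires the investigator to follow every AE until it resolves, settles or the subject is lost.

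**The concern.** The rule turns a missing end date into a number and then handles that number like any observed duration. Which number depends on a term the reader has to guess at. If the date falls at the end of follow-up, a mild symptom last recorded in the first week is reported as a reaction lasting about half a year. If the date is an early withdrawal, the time at which observation stopped is reported as the time at which the symptom stopped.

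Safety and tolerability are the primary objective, and duration by arm is part of how readers judge tolerability. One such value can set an arm's maximum and shift its mean for reasons of follow-up status. The 18 to 49 cohort is the most exposed, with only 16 subjects per arm.

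**Working it through.** **1. The SAP's own convention.** The worked example in SAP 6.5.1.1 has fatigue from Day 2 to Day 3 and again from Day 7 to Day 9. End day minus onset day, summed, gives (3 − 2) + (9 − 7) = 3, which matches the stated 3. The convention is therefore end day minus onset day, with no added day.

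**2. Inputs.** Onset lies between Day 1 and Day 7 (SAP 6.5.1.1). Planned follow-up ends at Day 180 (Protocol 3.3), and the Month 6 call has a window of ± 5 days (Protocol 6.1.6). Scheduled contacts before that include Days 8, 15 and 29.

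**3. Duration given to one event with no stop date, by reading of the discontinuation date.**

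| End date used | Onset Day 7 | Onset Day 1 |
|---|---|---|
| Last visit Day 8 | 8 − 7 = 1 | 8 − 1 = 7 |
| Last visit Day 15 | 15 − 7 = 8 | 15 − 1 = 14 |
| Last visit Day 29 | 29 − 7 = 22 | 29 − 1 = 28 |
| Day 180 (completion, or about when loss to follow-up is determined) | 180 − 7 = 173 | 180 − 1 = 179 |
| Day 185 (upper end of the Month 6 window) | 185 − 7 = 178 | 185 − 1 = 184 |

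A subject last seen on Day 8 with a Day 7 onset can thus be given 1 day or 173 days.

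**4. Subjects for whom the date does not exist.** Under Protocol 5.19, discontinuation means stopping before the Day 180 visit, so a completer has no discontinuation date. The rule is then undefined, unless completion is substituted, which gives the Day 180 row. At the Day 29 Analysis (SAP 2.7) most subjects are still in follow-up. If duration is among the outputs chosen for that analysis, the rule cannot be applied to them as written, and the same event could take a different value at the final lock.

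**5. Effect on an arm's summary.** The documents give no rate of missing stop dates and no expected durations, so this is an illustration. Assume n subjects in an arm report the event, all but one with a mean of 2 days, and the last is given 173 days. The mean is ((n − 1) × 2 + 173) / n.

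- n = 10: (18 + 173) / 10 = 19.1 days
- n = 20: (38 + 173) / 20 = 10.55 days
- n = 60: (118 + 173) / 60 = 4.85 days
- n = 100: (198 + 173) / 100 = 3.71 days

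The maximum is at least 173 in every case. If the same event ended at Day 29 (22 days), the mean with n = 60 would be (118 + 22) / 60 = 2.33 days.

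**The case against.** A reader might infer that every subject lost to follow-up is given about 173 days because the discontinuation date is fixed only after Day 180. The documents do not say that. Protocol 5.19 fixes when the lost status is determined, not which calendar date is recorded. Its definition of Early Discontinuation, and the last-visit convention in SAP 5.2, both leave room for an earlier date. The long durations are one possible reading.

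A reader might also infer that nobody can know about a continuing symptom after Day 29. Protocol 7.4 requires AEs to be followed to resolution or loss, and Protocol 5.18 and 5.21 tie completion to the required safety follow-up, with queries resolved before the study closes. For a completer, a blank stop date after cleaning may therefore mean that the event really is ongoing.

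Other points against the concern also stand:

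- An event that ends within the diary takes its end from the grade returning to 0 and needs no stop-date field. The rule mainly reaches events still present when the 7-day diary closes.
- Duration carries no [P] tag and is not tested. The primary percentages do not depend on it.
- SAP 6.2.1 already plans the median, which one outlier among many reporters barely moves, and by-subject listings would let an extreme value be traced.
- Nothing suggests that missing stop dates would differ systematically between arms of a randomised, observer-blind study. The likely effect is noise, not directional bias.

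These points limit the impact. They do not supply the missing definition, and they do not make an unresolved time an observed one. The planned mean and maximum remain exposed.

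**Conclusion.** The point holds as a defect in a stated derivation rule. The end date is undefined, it does not exist for completers, and at the Day 29 Analysis it would not exist for most subjects. Depending on the reading, one missing stop date gives 1 to 14 days for a subject lost after the Day 8 or Day 15 contact. It gives 173 to 179 days if the date is completion or the determination of loss to follow-up, taken as Day 180. On every reading, a time that was cut off or is unknown enters the table as a completed duration.

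The shifts in the mean rest on assumed numbers of reporters and a 2-day typical duration. The ranges of days rest only on the SAP's convention and the visit schedule. The correction is worth making before the tables are produced, but it concerns a descriptive tolerability summary and leaves the primary endpoints untouched.

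**What to change.** In SAP 6.5.1.1, replace the study discontinuation date with: *the last date on which the event was recorded as present or its status was assessed (last diary entry or last AE contact, including any later follow-up under Protocol 7.4)*. Apply this to completers and discontinued subjects alike, and at both the Day 29 and Final Analyses.

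Flag these durations as minimum (censored) values and show their number by arm. Present the mean and maximum of resolved events separately from the flagged ones, alongside the median already planned. A Kaplan-Meier summary is not proposed: the SAP adds up separate occurrences, so a total containing one unresolved episode is not ordinary time-to-resolution data.

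The cost is a short SAP edit and minor extra programming, with no change to data collection. The downside is that a few durations will read as at least x days.

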6.5.1.2. Unsolicited Adverse Events

An unsolicited AE is an AE that is spontaneously reported by the subject or discovered by the Investigator. New onset of chronic illness(s) would be recorded as part of the collection of unsolicited AEs as specified in the visit procedures. Unsolicited AEs are collected separately from solicited AEs.

Solicited AEs continuing beyond 7 days will be flagged using rules given in Section 5.2 and described in separate summaries as explained in Section 6.5.1.3.

The definition of a treatment emergent AE (TEAE) is an event that occurs after vaccination and within the 28 days after vaccination (i.e., excluding those after a subject has given informed consent, but before vaccination):

- Onset (days) = Start date of AE – Date of Study Vaccine Administration + 1
- An AE is a TEAE if:
 - Onset \geq 1 and Onset \leq 28
 - For AEs with Onset=1 the time of onset of AE must be greater or equal to the time of vaccination to be considered a TEAE

Adverse events are summarized by subject, therefore, in any tabulation, a subject contributes only once to the count for a given adverse event (SOC or preferred term).

Unsolicited AEs will be coded using the Medical Dictionary for Regulatory Activities (MedDRA) and will be summarized by decreasing frequency of SOC and preferred term within SOC in the control group, as follows:

- [P] Any unsolicited TEAEs
- Possibly or probably related unsolicited TEAEs
- Unsolicited TEAEs leading to study withdrawal
- Any AE leading to death
- [P] Any SAE within 6 months after the vaccination by maximum relationship to study treatment. This summary will include serious solicited AEs.
- [P] Any NOCI within 6 months after the vaccination by maximum relationship to study treatment.
- [P] Any MAAEs within 6 months after the vaccination by maximum relationship to study treatment.

Following by-subject Listings will be provided:

- Pre-vaccination AEs (non-emergent)

- All unsolicited TEAEs
- All Serious post-vaccination AEs, NOCIs and MAAEs

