## 7 SAFETY

### 7.1 Definitions

#### 7.1.1 Adverse Event

An adverse event is any untoward medical occurrence in a study subject, regardless of the suspected causal relationship with study vaccine.

The definition of an AE includes:

- A new-onset symptom or disease
- An exacerbation of a pre-existing symptom or disease
- A new-onset laboratory abnormality considered by the Investigator to be clinically significant
- A new-onset symptom or disease that occurs as a result of a protocol-specified procedure

The definition of an AE does **not** include:

- A pre-existing symptom or disease that does not worsen during the study (even if first disclosed by the subject after the start of the study)
- A medical or surgical intervention such as surgery, endoscopy, tooth extraction, or transfusion (although the condition leading to the procedure or a complication from the procedure may be an AE)
- An uncomplicated pregnancy
- A dosing error without any resulting signs or symptoms
- Any other situation where an untoward medical occurrence has not occurred (eg, hospitalization for cosmetic elective surgery or social admissions)

The definition of a treatment emergent AE (TEAE) is an event that occurs after vaccination and within the 28 days after vaccination (ie, excluding those after a subject has given informed consent, but before vaccination).

The definition of a NOCI includes:

A new-onset of chronic illness is a disease or condition, that is newly diagnosed, requires ongoing medical attention and/or limits activity of daily living, eg, heart disease, cancer, diabetes.

The Investigator will attempt to establish a diagnosis based on signs, symptoms, and other clinical information. Whenever possible, the Investigator will report an AE as a diagnosis rather than one or more signs or symptoms. If a clinically significant laboratory abnormality meets the

definition of an AE, a diagnosis or clinical signs and symptoms rather than the abnormal laboratory finding should be reported if possible. If no diagnosis is known and clinical signs and symptoms are not present, but the laboratory abnormality is clinically significant by itself, then it should be reported as the AE.

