## 9 STATISTICAL ANALYSIS

This Phase 1/2a study is designed to achieve both safety and immunogenicity objectives.

The primary objectives are to evaluate the safety of a single injection of VAX-24 at three dose levels, and to compare the safety of VAX-24 to that of PCV20 administered to two control groups: 1) subjects 18 to 49 years of age receiving PCV20; and 2) subjects 50 to 64 years of age receiving PCV20.

The secondary immunogenicity objectives are to assess the induction of OPA and IgG antibody responses by VAX-24 at three dose levels compared to the 20 PCV20 serotypes (1, 3, 4, 5, 6A, 6B, 7F, 8, 9V, 10A, 11A, 12F, 14, 15B, 18C, 19A, 19F, 22F, 23F and 33F), as measured at 28 days after the injection (Day 29) and 4 non-PCV20 serotypes (2, 9N, 17F, 20B), measured at 28 days after the injection (Day 29) for subjects aged 50 to 64 years.

Endpoints will be analyzed by age group (18 to 49, 50 to 59, 60 to 64, and 50 to 64 years of age). Safety will also be summarized for all subjects combined (18 to 64 years of age).

A statistical analysis plan will be generated and approved prior to the data freeze and treatment group unblinding for the primary safety and secondary immunogenicity endpoints through Day 29 visits. Individual treatment unblinding will occur after the data is cleaned through the last Month 6 visits and final database lock. A single completed Clinical Study Report (CSR) will summarize safety findings through Month 6 for all 864 subjects and immunogenicity for 800 subjects 50 to 64 years of age.

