### 9.6.3 Unsolicited AEs

All the unsolicited AEs occurring during the study will be recorded, regardless of their assessment of relatedness by the Investigator.

The original verbatim terms used by Investigators to identify AEs in the eSD will be mapped to preferred terms using the MedDRA dictionary. The unsolicited AEs will then be grouped by MedDRA preferred terms into frequency tables according to system organ class (SOC). All reported AEs, as well as AEs judged by the Investigator as at least possibly related to study vaccine, will be summarized by treatment group, according to SOC and preferred term within SOC. When an unsolicited AE occurs more than once for a subject, the maximum severity reported and strongest reported relationship to the treatment group will be counted.

---

Only TEAEs will be summarized as defined in [Section 7.1.1](#). The selection of unsolicited AEs and their assignment to time intervals will be done by day of onset and not by days ongoing/persisting.

Unsolicited AEs will be summarized by alphabetic SOC and preferred term as follows:

- Any unsolicited TEAE
- Possibly or probably related unsolicited TEAEs
- SAEs
- Possibly or probably related SAE
- Unsolicited TEAE leading to withdrawal
- Any AE leading to death

Listings of all TEAEs will be provided by subject.

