2. STUDY DESIGN

2.1. Introduction

This Phase 1/2a parallel-group, randomized, observer-blind study is to be conducted in two populations of healthy adults, 18 to 49 years of age and 50 to 64 years of age. Subjects will be randomly assigned in a 1:1:1:1 ratio to receive either VAX-24 at one of three dose levels or the active comparator.

A Phase 1 cohort of 64 subjects (16 for each VAX-24 dose group and 16 for the comparator group) aged 18 to 49 years will be enrolled initially. Subjects will receive VAX-24 or PCV20 on Day 1. All subjects will have safety labs analyzed at Baseline and 28 days post-vaccination (Day 29). Solicited adverse events (AEs) will be collected for 7 days post-vaccination and unsolicited safety information for 28 days post-vaccination, with serious adverse events (SAEs), new onset of chronic illness (NOCI) and medically attended adverse events (MAAEs) collected up to 6 months post-vaccination. A defined safety review of data (solicited and unsolicited AEs, and SAEs) through 7 days post-vaccination will occur by an independent DMC before proceeding with enrollment of the remaining subjects, adults 50 to 64 years of age.

Subjects in the 50-to-64-year-old group will receive VAX-24 or PCV20. Solicited and unsolicited AEs will be collected similarly to the subjects aged 18 to 49 years described. All subjects in this age group will have blood samples drawn for immunogenicity analysis (Opsonophagocytic antibody (OPA) and Immunoglobulin G (IgG)) at Days 1, 29.

Approximately 100 of the 800 subjects from 50 to 64 years of age will be consented for collection of additional blood samples (up to 32 mL per draw) by a limited number of clinical sites; subjects will have blood samples drawn at Days 1 and 29 to further characterize the immune response to PCVs.

The schedule of assessments is in Appendix A, further details available in the study protocol.

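### The SAP's TEAE rule stops 27 days after vaccination, one day short of the 28-day definition it implements

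*SAP*

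**What the plan says.** SAP Section 6.5.1.2 first words a TEAE as an event after vaccination and within the following 28 days. It then gives the programming rule: onset in days is the AE start date minus the vaccination date plus 1, and an AE qualifies if "Onset \geq 1 and Onset \leq 28".

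The worded definition comes from Protocol Section 7.1.1: "an event that occurs after vaccination and within the 28 days after vaccination". Protocol Section 9.6.3 ties the unsolicited AE summaries to it ("Only TEAEs will be summarized as defined in" Section 7.1.1) and adds: "The selection of unsolicited AEs and their assignment to time intervals will be done by day of onset".

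Three other places show which study day the documents mean by 28 days:

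- Protocol Section 9, on antibody responses: "as measured at 28 days after the injection (Day 29").
- SAP Section 2.1, on safety laboratory tests: "All subjects will have safety labs analyzed at Baseline and 28 days post-vaccination (Day 29").
- Protocol Section 7.5.1: "The reporting period for unsolicited AEs is immediately after study vaccine administration on Day 1, continuing through Day 29".

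SAP Section 7 states that the planned analyses do not differ from those in the protocol.

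**The concern.** The programming condition does not match the sentence directly above it. Because vaccination day is counted as 1 rather than 0, a limit of 28 on the onset variable cuts off one calendar day earlier than a limit of 28 days after vaccination.

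The rule feeds a primary safety output. An AE that starts on Day 29 and is not serious, a new-onset chronic illness (NOCI), medically attended (MAAE) or fatal would be collected but left out of:

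- the unsolicited TEAE table, which the SAP marks as primary;
- the tables of related TEAEs and of TEAEs leading to withdrawal;
- the combined solicited and unsolicited table in SAP Section 6.5.1.3;
- the unsolicited TEAE listing.

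It would fit neither of the other two listings named in SAP Section 6.5.1.2, which cover pre-vaccination AEs and serious, NOCI and MAAE events. A programmer following the SAP would therefore produce a count that differs from the protocol-defined one, with nothing in SAP Section 7 to say so.

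SAEs, NOCIs and MAAEs are still tabulated through 6 months, and deaths without a TEAE restriction. Outputs on solicited AEs continuing beyond 7 days are unaffected, because those events start in the first week.

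**Working it through.** **Day count**

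Input: the SAP formula, onset = AE start date − vaccination date + 1.

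- The documents' own label: 28 days after vaccination gives 28 + 1 = 29. This reproduces the Day 29 label in Protocol Section 9 and SAP Section 2.1.
- The SAP limit: onset 28 gives 28 − 1 = 27 days after vaccination.
- An event 28 days after vaccination has onset 29, which exceeds 28, so it is excluded.
- With a limit of 29: 29 − 1 = 28 days after vaccination. An event 29 days after vaccination has onset 30 and stays out.

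The shortfall is exactly one day. The rule covers 28 of the 29 calendar days from Day 1 through Day 29, so it drops 1/29 = 3.4% of them.

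**Illustrative effect on the primary percentage**

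The documents give no unsolicited AE rates. I assume that a proportion p of subjects has at least one unsolicited AE through Day 29, with constant daily risk. The proportion counted under the SAP rule is then 1 − (1 − p)^(28/29).

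| Assumed p | Counted | Loss (points) | Subjects per 200 | Subjects per 16 |
|---|---|---|---|---|
| 10% | 9.672% | 0.328 | 0.66 | 0.05 |
| 20% | 19.382% | 0.618 | 1.24 | 0.10 |
| 30% | 29.134% | 0.866 | 1.73 | 0.14 |

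Within this model these are upper bounds, because every subject is taken to be under general AE collection for all of Day 29.

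**If collection ends at the visit**

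The Day 29 visit has a window of ±3 days, that is Days 26 to 32 (7 days). The later calls in Protocol Section 6.1.6 cover only SAEs, NOCIs and MAAEs. If visits are spread evenly and general collection stops at the visit, the 3/7 of subjects seen on Days 26 to 28 are already past collection. The other 4/7 are still covered on Day 29.

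| Assumed p | Loss (points) | Subjects per 200 |
|---|---|---|
| 10% | 0.328 × 4/7 = 0.187 | 0.37 |
| 20% | 0.618 × 4/7 = 0.353 | 0.71 |
| 30% | 0.866 × 4/7 = 0.495 | 0.99 |

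This still gives subjects seen on Day 29 a full day of collection. Leaving them out (3/7 instead of 4/7) gives 0.28, 0.53 and 0.74 subjects per 200.

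**The case against.** The best defence is that the SAP counts days inclusively. For solicited AEs, SAP Section 6.5.1.1 analyses events "within 7 days after vaccine administration (i.e. from Day 1 to Day 7"), repeats that span for maximum severity, and gives an onset range of 1 to 7. Protocol Section 5.11 likewise collects them for 7 days starting on Day 1. Counted that way, Days 1 to 28 are 28 days. The Day 29 labels in Protocol Section 9 and SAP Section 2.1 describe blood draws, not an AE window. A collection period through Day 29 also does not by itself force an analysis window of the same length: SAEs are collected from consent, while TEAEs start at vaccination.

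This shows how the rule may have arisen, but it does not reconcile the text. The inclusive count is not applied uniformly: SAP Section 3.2 describes solicited AEs as running up to Day 8. It also contradicts the documents' own equation of 28 days with Day 29, and it leaves a day of collected unsolicited AEs outside the analysis without saying so.

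Three points on size do stand. First, the effect is below one percentage point only under the assumed rates and constant risk. If risk is concentrated soon after vaccination the loss is smaller. If onset dates cluster on the Day 29 visit it could be larger, for example through laboratory AEs dated to that day's draw; the documents give no dating convention, so this cannot be quantified. Second, other outputs cover part of the gap: withdrawal reasons appear in the disposition table and listing, and Day 29 laboratory abnormalities appear in the shift table and laboratory listing. Third, no comparison between arms is shown to change.

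**Conclusion.** The concern holds. By the SAP's own formula the TEAE window ends 27 days after vaccination, while the definition it implements says 28. The mismatch of one day is exact and needs no assumption. That 28 days means Day 29 rests on the documents' own labels and on the reporting period in Protocol Section 7.5.1.

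The practical effect is probably small: 1 of 29 days, and between about 0.3 and 1.7 subjects per 200-subject arm across the assumed scenarios. The rule is identical in all arms and the safety analysis is descriptive, so there is no evident bias between groups. It should still be corrected, because it determines a primary safety table and departs from the protocol definition without being declared.

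**What to change.** In SAP Section 6.5.1.2, change the condition to onset from 1 to 29 inclusive. Equivalently, require start date minus vaccination date to be from 0 to 28. Keep the existing time-of-day check for events on the vaccination date. Make the change before the interim database lock for the Day 29 Analysis.

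If the sponsor did intend Days 1 to 28, the SAP should instead say that vaccination day is the first of the 28 days. The TEAE definition and the reporting period in both documents would then have to be aligned with that, and the difference entered in SAP Section 7. The first option is simpler and leaves the protocol unchanged.

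The cost is one programming condition and one line of SAP text. Reported unsolicited AE percentages may rise slightly in all arms.
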